12.2 Biological Correlative Studies Sample Instructions

Subjects will have the following required urine samples sent.

12.2.1 Required Urine Polyamines Collection:

At screening, on Days 1 and 15 of Cycle 1, and on Day 1 of cycles 2-27, urine polyamines will be collected.

- A. First morning void urines will be collected using a clean catch method in containers and placed at 4°C until transported to the laboratory. Collection of 15ml is ideal, but lab can accept amounts down to a minimum of 1 (one) ml.
- B. Specimens will be transferred to 15ml polypropylene conical tubes (use multiple 15ml tubes as needed) and stored at -80°C until analysis for the dc-SAM and polyamines. Samples should be kept at 4°C (either in refrigerator or on ice pack during shipping) until frozen and must be frozen within 48 hours from collection time. If unable to freeze within 48 hours please note this on the container along with time before frozen.

- C. Samples will be batch shipped on a Monday (send after approximately 20 samples are collected) and sent on dry ice to:

[name]

Pediatric Oncology Translational Research Laboratory

Coopers Landing

[name]

[name]

Ph: [contact]

[contact]

Subjects will have the following optional (recommended) blood and bone marrow samples sent.

12.2.2 Optional Blood Collection

1. Sample One, Two, and Three-

- A. Sample 1- On Day 1: 2 mls of blood will be collected in an EDTA tube (s). At the time of collection, the tube should be gently inverted 6-8 times.
- B. Sample 2- On Days 1 and 15 of Cycle 1, Day 1 of cycles 2 through 12, and 14, 17, 21, 24 and off -therapy- 5 mls of blood will be collected in an EDTA tube(s). At the time of collection, the tube should be gently inverted 6-8 times.
- C. Sample 3- On Days 1 and 15 of Cycle 1, Day 1 of cycles 2 through 12, and 14, 17, 21, 24 and off-therapy- 5 mls of blood will be collected in an EDTA tube(s). At the time of collection, the tube should be gently inverted 6-8 times.
- D. Shipment/Storage will be as follows:
Specimens A-C above should be placed on ice immediately upon draw and sent on an ice pack immediately via FED-EX overnight. (If Friday collection site may store in refrigerator and ship on Monday). Ship to:

[name]

Pediatric Oncology Translational Research Laboratory
Coopers Landing
[name]
[name]
Ph: [contact]
[contact]

2. A 7.5cc whole blood specimen will be collected in a BD CPT Vacutainer tube(s) containing the anti-coagulant Sodium Heparin (BD Cat no. REF362753, 8mL draw capacity).

- A. At screening and then start of cycles 3, 6, 12, 14, 17, 21, 24 and off-therapy.
- B. Specimen Handling:
1. If BD CPT Vacutainer tube is not available at the site, collect blood in a Green top heparin tube (do not use glass tubes). Do not follow steps 2-5- Ship without processing in the green top tube. Skip to C below for shipping instructions.
 2. After collection, store tube upright at room temperature until centrifugation. Blood samples should be centrifuged within two hours of blood collection.
 3. Centrifuge tube/blood sample at room temperature (18-25° C) in a horizontal rotor for a minimum of 15 minutes
 4. at 1500 to 1800 RCF (Relative Centrifugal Force).
NOTE: Remix the blood sample immediately prior to centrifugation by gently inverting the tube 8 to 10 times. Also, check to see that the tube is in the proper centrifuge carrier/adaptor.
 5. After centrifugation, mononuclear cells and platelets will be in a whitish layer just under the plasma layer. These tubes are now ready for transportation. If not transporting immediately, they can be stored at room temperature until transportation. Samples should be shipped at room temperature.

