3.0 Study Objectives

3.1 Primary Objective:

3.1.1 To evaluate the preventative activity of DFMO as a single agent in patients that are in remission based on: Event free survival (EFS)

3.2 Secondary Objectives:

3.2.1 Correlation of urinary polyamine levels with progression of disease in neuroblastoma.

3.2.2 To evaluate the preventative activity of DFMO as a single agent in patients with neuroblastoma who are in remission based on:

- Overall Survival (OS)

3.2.3 To continue to determine the safety and tolerability of DFMO as a single agent and in pediatric and young adult patients with high risk neuroblastoma that is in remission.

3.2.4 To evaluate the pharmacokinetics (PK) of new DFMO formulation in a minimum of 10 patients.

3.2.5 Biological Correlates to minimally include: 1) Urine: polyamine levels and blood inflammatory markers, 2) Blood- microRNA analysis as predictor of DFMO effect; ODC SNP analysis in DNA isolated from nucleated cells; circulating tumor cell analysis, and explorative biomarker analysis 3) Bone Marrow- flow cytometry of minimal residual disease of tumor; explorative biomarker analysis

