7.5 Treatment Phase – Cycles 13-27

All Cycles will be 28 days in duration without interruption. The following procedures must be completed:

Cycle 13-27 Day 1

The following procedures may be performed up to +/- 5 days from Day 1:

1. Medical History and Physical examination (including body weight), including documentation of an update of all previous abnormalities, any new abnormalities.
2. Vital signs, including temperature, pulse rate, blood pressure (sitting);
3. Review and recording of concomitant medications;
4. Monitoring and documentation of all AEs and review of concurrent illnesses
5. BSA calculation (from body weight and height);

6. ECOG Performance status/Lansky Play status (Appendix I);
7. Urine for Vanillylmandelic Acid (VMA) & Homovanillic Acid (HVA)
8. Urine for Biological Correlates per section 12.0
9. Urine or serum pregnancy test for female subjects of child bearing potential (onset of menses or ≥ 13 years of age);
10. Collection of previous cycle drug dosing diary and dispensing of new drug dosing diary

Additionally at the start of cycles 14*, 17, 21*, 24, and at off therapy (end of cycle 27)

Windows- The following should be done within +/-5 days of the start of specified cycle. For off-therapy/end of cycle 27 they should be done within 30 days (+7) after stopping study drug:

1. CBC with differential;
2. Serum electrolytes, blood urea nitrogen (BUN), creatinine, bilirubin, LDH, ALT, and AST;
3. C-reactive protein (CRP) and Erythrocyte sedimentation rate (ESR)
4. Optional: Blood for Biological Correlates per section 12.0 (additional consent required)
5. Optional: Blood for Biological Correlates (Circulating Tumor Cells to Houston, TX) per section 12.0 (additional consent required).

* Start of cycles 14 and 21 bloodwork stated above can be done at the same time as the IV is placed for the scans done at the end of cycles 13 and 20 in order to reduce the amount of venipuncture the subject experiences.

End of Cycles 3, 6, 9, 13, 20 and off therapy (cycle 27) – scans may be done more often per institutional standards.

Windows- Scans should be done within +/-14 days of the start of next cycle. Off therapy/end of cycle 27 scans should be done within 30 days (+7) after stopping study drug.

1. MIBG scan (for MIBG avid subjects only). Consider PET scan for non MIBG avid subjects.
2. CT/MRI (use same radiologic method as baseline)

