7.9 Off-Therapy / 30 Day Follow-up Visit

Subjects will return to the clinic 30 (+7) days after the last dose of DFMO, and the following evaluations will be conducted:

1. Medical History and Physical examination (including body weight), including documentation of an update of all previous abnormalities, any new abnormalities, and a detailed neurological exam;
2. ECOG Performance status/Lansky Play status (Appendix I);
3. Vital signs, including temperature, pulse rate, blood pressure (sitting);
4. Review and recording of concomitant medications;
5. Monitoring of AEs and review of concurrent illnesses
6. Collect previous cycles drug dosing diaries (if not collected already)

Any subject with a suspected study drug-related toxicity at the follow-up visit must be followed until all current adverse events have resolved to baseline or \leq grade 2. This may require additional clinical assessments and laboratory tests. The follow-up results will be recorded on the appropriate page of the CRF, as well as in the subject's source documentation. Subjects that have started a new anti-cancer treatment since going off DFMO will be censored from any further AE collection at the date of starting the new therapy.

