9.0 Patient Withdrawal and Trial Discontinuation

9.1 Criteria for Subject Off-Therapy

Subjects may be withdrawn from the study treatment for the following reasons:

- Subject completes all protocol defined therapy- 27 cycles
- Relapsed neoplastic disease
- Subject or guardian withdraws consent to continue study drug
- Subject develops an intercurrent illness that precludes further participation, or requires a prohibited concomitant treatment
- The Investigator withdraws the subject in the subject's best interests
- Subject is lost to follow-up (defined as the inability to contact the subject on 3 separate occasions over a period of 2 weeks)
- Administrative reasons (e.g., the subject is transferred to hospice care)
- An adverse event, which in the opinion of the Investigator, precludes further trial participation or fulfills the protocol requirements for withdrawal (e.g., the development of dose limiting toxicity despite a reduction in protocol therapy for a previous episode of dose limiting toxicity)
- Death

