The sequential biomarker data over the course of treatment for each patient will be classified as elevated or not based upon the following *a priori* study criteria and blinded to patient progression status. Elevation of the biomarker is defined as diacetylspermine levels > 500nmol/gm creatinine on 2 consecutive urine levels. The biomarker prevalence rates for the patients who progress (estimated to be n= 38) and those who do not progress (estimated n=89) over the two years of the trial treatment will be compared using a Fisher's exact test of the equality of the two EFS prevalence rates implemented with a 5% two-tailed Type I error level. A 95% exact confidence interval for the absolute difference in prevalence rates along with a 95% exact confidence interval for the odds ratio for the resulting prevalence rates will be obtained to complement the formal hypothesis testing. Since OS will also be a secondary outcome for comparing the utility of the biomarker prevalence, time-to-event analyses will also be implemented using the Kaplan-Meier approach initially using the *a priori* biomarker definition. These initial time-to-event analyses will then be supplemented with a Cox proportional hazard modeling effort using the quantitative biomarker assessment to allow for an exploratory analysis of other cut-point definitions that can be used to contrast with that of the original *a priori* definition. Potential confounding clinical measures that are identified for the recurrent and non-recurrent patients will be incorporated in a limited fashion using Cox proportional hazard models that also include the biomarker effect. This exploration of confounders will need to be limited due to the anticipated small sample sizes. Data from this stratum will guide the statistical design for a Phase II study in this patient population.

Stratum 2:

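### Off-therapy correlate blood has no rule placing it before new anticancer therapy, and no urine is scheduled at relapse or off-therapy, so some relapsers cannot meet the two-consecutive-urine biomarker definition

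*Combined protocol and SAP*

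**What the plan says.** **Blood.** Section 12.2.2 places the two 5 ml optional samples at "Day 1 of cycles 2 through 12, and 14, 17, 21, 24 and off -therapy- 5 mls of blood will be collected", and the tumor-cell tube at off-therapy as well. It gives no timing for that point. The only window is in Section 7.5: "For off-therapy/end of cycle 27 they should be done within 30 days (+7) after stopping study drug".

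**Leaving therapy.** Section 9.1 lists "Relapsed neoplastic disease" as a reason to stop study treatment. Section 7.9 sets the off-therapy visit at 30 (+7) days and provides that "Subjects that have started a new anti-cancer treatment since going off DFMO will be censored from any further AE collection", from the date the new treatment starts. Nothing comparable is stated for correlate samples.

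**Urine.** Section 12.2.1 sets the required schedule: "At screening, on Days 1 and 15 of Cycle 1, and on Day 1 of cycles 2-27, urine polyamines will be collected". The off-therapy lists in Sections 7.5 and 7.9 contain no correlate urine, and its Follow Up cell in the Procedures and Assessments table is blank. The cycle visits have a window: "The following procedures may be performed up to +/- 5 days from Day 1".

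**Use of the urine.** A secondary objective in Section 3.2 is "Correlation of urinary polyamine levels with progression of disease in neuroblastoma". For Stratum 1 the rule is "Elevation of the biomarker is defined as diacetylspermine levels > 500nmol/gm creatinine on 2 consecutive urine levels". Subjects who progress and subjects who do not are then compared by Fisher's exact test.

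**The concern.** Two gaps affect what is measured around relapse.

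The off-therapy blood may be taken after a relapsed subject has begun other treatment. Protein, microRNA and tumor-cell results from such a sample may describe the new treatment as well as the relapse.

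The urine gap touches a comparison that the plan has powered. A subject who stays on treatment and has one raised urine gives another about 28 days later, which can confirm it. A subject who relapses in between stops DFMO and has no further scheduled urine, so the same first raised value counts as not elevated. Completers face this only at the cycle 27 urine. The misclassification therefore falls mainly on the relapse group, lowers its observed prevalence and pulls the comparison toward no association. Samples not taken at relapse cannot be recovered later.

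**Working it through.** **1. The plan's own figure.** Inputs from Section 10 (Stratum 1): 38 relapse and 89 non-relapse subjects, prevalence 60% and 30%, Fisher's exact test, two-sided 5%. Full enumeration of the two binomials gives a power of 86.8%. This agrees with the 85% in Section 10 and the at-least-85% in the synopsis. The sample size is not in dispute.

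**2. Blood window.** Latest draw = 30 + 7 = 37 days after the last dose. This is an outer limit; a draw on the day DFMO stops also complies.

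**3. Spacing of urines.** Nominal 28 days. With a 5-day window on each side, consecutive Day 1 urines can be 28 - 10 = 18 to 28 + 10 = 38 days apart. In cycle 1 the nominal spacing is 14 days (Day 1, Day 15, next Day 1).

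**4. Chance of two consecutive raised urines before relapse.** Assumptions, not in the documents: the rise starts L days before relapse and persists; relapse is uniform between visits; spacing is exactly 28 days. Let U, uniform on 0 to 28, be the days from the last urine to relapse.

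- Plan: both of the last two urines are raised if U + 28 ≤ L, so the probability is (L - 28)/28, limited to 0 to 1.
- With one urine at relapse: the last scheduled urine must be raised, U ≤ L, so the probability is L/28, limited to 0 to 1.

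| Lead L (days) | Plan | With relapse urine | Loss |
|---|---|---|---|
| 14 | 0% | 50% | 50 points |
| 28 | 0% | 100% | 100 points |
| 42 | 50% | 100% | 50 points |
| 56 | 100% | 100% | 0 |

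Simulating each visit uniformly within its ±5-day window gives 0% against 50%, 6% against 94%, 50% against 100%, and 94% against 100%. The pattern is the same.

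**5. Relapse found close to a Day 1 urine.** Section 7.5 places scheduled scans within ±14 days of the start of the next cycle. If relapse is identified at a Day 1 visit and that urine is taken (assumed, with the same ±5-day jitter), the plan already captures about 50% at a 28-day lead and 100% at 42 days. The loss is then much smaller than in step 4.

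**6. What missed elevations would do to power.** Suppose a fraction of truly elevated relapsers is missed (assumed) and the non-relapse prevalence stays at 30%:

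| Missed | Relapse prevalence | Exact power |
|---|---|---|
| 0% | 60% | 86.8% |
| 10% | 0.60 × 0.90 = 54% | 69% |
| 20% | 0.60 × 0.80 = 48% | 45% |
| 30% | 0.60 × 0.70 = 42% | 23% |

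These rows show sensitivity only. The documents give neither the missed fraction nor whether the 60% already allows for it.

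**The case against.** - **The planned test does not need a relapse-day sample.** It classifies sequential on-treatment urine, and the blood correlates are voluntary with no stated off-therapy comparison. This stands: the test can be run as written, and no formal blood analysis is invalidated. It does not remove the asymmetry in who can supply a second raised value.
- **The 37-day window may apply only to completers**, since Section 7.5 couples off-therapy with the end of cycle 27. That reading is possible. Early relapsers would then have no stated window, which is no safer.
- **A reader might infer that most relapse blood is contaminated.** If new therapy starts on day 7, 14 or 21 and draws are uniform over days 0 to 37, (37 - s)/37 gives 81%, 62% or 43%. Neither assumption is in the documents, and sites may draw at once. The text supports only that some samples may be affected.
- **A reader might also infer that a rise beginning less than 28 days before relapse can never appear on two consecutive urines.** The visit windows and the cycle 1 spacing in step 3 rule that out, and scans near Day 1 soften the loss.
- **Marrow is an exception.** Sections 7.5 and 12.2.3 allow optional research marrow when progression is suspected. That stands, but marrow does not replace urine or blood.
- **Parts of Section 12 are redacted or missing from the copy reviewed**, so a protective rule there cannot be excluded. The visible schedules all agree.

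**Conclusion.** The point holds as a cheap improvement to a secondary objective. Three facts are firm: the off-therapy blood may be drawn up to day 37, or has no stated window for early relapsers; no visible rule ties it to the period before new anticancer therapy; and no urine is scheduled at relapse or off-therapy while the biomarker requires two consecutive raised values. The direction of the urine effect, toward no association, follows from the design, given a rise that precedes relapse.

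Its size does not follow from the documents. It could be large for leads of about 14 to 42 days, is negligible from 56 days, and is smaller when relapse is found near a Day 1 urine. The effect on blood cannot be quantified. Primary EFS, the sample size and optional marrow sampling at suspected progression are unaffected.

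**What to change.** In Sections 7.5 and 12.2 and the Procedures and Assessments table:

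1. Time the off-therapy correlate blood at identification of relapse or at DFMO stop and, where possible without delaying care, before any new anticancer therapy. State that this covers early stoppers as well as completers.
2. Add one urine at the same point for every subject, so that both groups are handled alike. Section 12.2.1 already accepts 1 ml.
3. In the Section 10 biomarker definition, state that this urine counts as a consecutive value.
4. Record days since last dose and the start date of any new therapy, and exclude samples drawn after that start from the correlate analyses.

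Cost: a minor amendment, the same optional blood draw taken earlier, one extra urine per subject, and a few excluded samples. Treatment and sample size do not change.

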12.2.3 Optional Bone Marrow Collection

If subject agrees to optional biology portion of study, additional bone marrow samples should be sent at the following time points:

(Please note that if subject has also signed to protocol NMTRC 00B, these samples should be sent under that study instead):

All Subjects- At Enrollment, Any time a bone marrow is done during protocol therapy, Early Withdrawal (if indicated), and per institutional standards after that.

Sample Collection-

Send green top (sodium heparin) tube(s) with a minimum of 2cc and preferably 5cc of bone marrow aspirate in them. The bone marrow samples should be shipped room temperature- but needs to be sent out same day priority overnight (must get there within 24 hours of the draw). Shipments are only accepted Monday through Friday, so Bone Marrow draw needs to be done and shipped out on Monday through Thursday only please.

Please contact the lab at the number below to let them know of pending arrival.

Bone marrow 2-5cc in green top (sodium heparin) tube(s) at room temperature and will be shipped FED-EX overnight to:

Flow Cytometry Lab of Spectrum Health
Attn: [name]
Lemmen-Holton Cancer Pavilion
[name]
[name]
[contact]

12.3 Sample Storage and Destruction

Samples collected for any studies performed in this protocol may be stored indefinitely to research scientific questions related to cancer and/or study drugs. The subject retains the right to have the sample material destroyed at any time by contacting the principal investigator.

Appendix I: Performance Status/Scores

Performance Status Criteria Karnofsky and Lansky performance scores are intended to be multiples of 10					
ECOG (Zubrod)		Karnofsky		Lansky*	
Score	Description	Score	Description	Score	Description
0	Fully active, able to carry on all pre-disease performance without restriction.	100	Normal, no complaints, no evidence of disease	100	Fully active, normal.
		90	Able to carry on normal activity, minor signs or symptoms of disease.	90	Minor restrictions in physically strenuous activity.
1	Restricted in physically strenuous activity but ambulatory and able to carry out work of a light or sedentary nature, e.g., light housework, office work.	80	Normal activity with effort; some signs or symptoms of disease.	80	Active, but tires more quickly
		70	Cares for self, unable to carry on normal activity or do active work.	70	Both greater restriction of and less time spent in play activity.
2	Ambulatory and capable of all self-care but unable to carry out any work activities. Up and about more than 50% of waking hours	60	Required occasional assistance, but is able to care for most of his/her needs.	60	Up and around, but minimal active play; keeps busy with quieter activities.
		50	Requires considerable assistance and frequent medical care.	50	Gets dressed, but lies around much of the day; no active play, able to participate in all quiet play and activities.
3	Capable of only limited self-care, confined to bed or chair more than 50% of waking hours.	40	Disabled, requires special care and assistance.	40	Mostly in bed; participates in quiet activities.
		30	Severely disabled, hospitalization indicated. Death not imminent.	30	In bed; needs assistance even for quiet play.
4	Completely disabled. Cannot carry on any self-care. Totally confined to bed or chair.	20	Very sick, hospitalization indicated. Death not imminent.	20	Often sleeping; play entirely limited to very passive activities.
		10	Moribund, fatal processes progressing rapidly.	10	No play; does not get out of bed.

*The conversion of the Lansky to ECOG scales is intended for NCI reporting purposes only.

References

